4.3.2 Exposure to rescue medication

The maximal total daily dose (insulin units) will be summarised using the Treated Subjects Data Set for the for the ST, ST+LT periods, and the Randomised Withdrawal Subjects Data Set for the randomised withdrawal period. For the ST period, the summary will include all rescue medication used up to the start of the LT period. For the ST+LT period the summary will include

all rescue medication used up to the last day in the ST+LT period (irrespective of whether the subject had early discontinued IP treatment). For the randomised withdrawal period the summary will include all rescue medication used from the randomised withdrawal baseline up to the last day in the randomised withdrawal period (irrespective of whether the subject had early discontinued IP treatment). Rescue treatment details will be listed as described in Section 4.2.5.

In addition, the number and percentage of subjects initiating rescue medication prior to Week 12 by categorical HbA1c ($< 7\%$, $\geq 7\%$) result at Week 12 will be summarised.

4.3.3 Compliance to IP treatment

Compliance to IP treatment will be summarised for the ST and ST+LT periods based on the Treated Subjects Data Set and for the randomised withdrawal period based on the Randomised Withdrawal Subjects Data Set, as the number and percentage of subjects with $< 80\%$, $\geq 80\%$ and $\leq 120\%$, and $> 120\%$ compliance. Study treatment compliance by subject and study period will be included in the corresponding listings for exposure to IP treatment.

4.4 Primary efficacy endpoint analysis

4.4.1 Primary analysis of the primary endpoint

The primary efficacy analysis will compare the mean reduction in HbA1c from baseline at Week 26 between overall drug treatment (low-dose and high-dose) and placebo. The ITT estimand (which will be estimated using data regardless of premature treatment discontinuation, regardless of rescue medication initiation and with multiple imputation) will be evaluated as the primary estimand.

Listings of HbA1c and FPG results used for the efficacy analysis will be presented with flags to identify data collected prior to rescue medication initiation or treatment discontinuation.

The primary efficacy analysis will be performed using an ANCOVA model, as described in Section 4.1.9. Separate models will be used for dapagliflozin and saxagliptin analyses, and each analysis will include the (common) placebo control. Each model will have terms for baseline HbA1c value, treatment group, and randomisation strata variables (age group, sex and background medication). Missing values for Week 26 will be imputed using multiple imputation method assuming the data are not missing at random. No weights will be used in the multiple imputation or ANCOVA for this analysis.

An overview of the analysis steps are as follows:

- i) Impute missing Week 26 HbA1c data using multiple imputation (as described in Section 4.1.12).
- ii) Analyse data by applying the ANCOVA model (described in Section 4.1.9) in each of the imputed data sets to calculate the LS means and corresponding SEs for the adjusted mean changes within each treatment group as well as for the differences in adjusted mean changes

between treatment groups. If any stratification variables in the imputation model are collapsed, then the ANCOVA model will be collapsed correspondingly.

- iii) Combine point estimates and SEs using Rubin's rules (as per Section 4.1.12.4) to produce valid global estimates with corresponding p-values and CIs.

Combined LS means and 95% confidence intervals for the mean change in HbA1c for each treatment group as well as the difference in the estimated mean change between the dapagliflozin/saxagliptin treatment group and placebo will be calculated. The p-value of the difference in Week 26 estimates between dapagliflozin/saxagliptin and placebo will be presented.

Both the MI-RD and wash-out imputation methods will be presented for the primary endpoint. If all of the imputation models have at least 5 observations, then MI-RD will be the primary analysis and wash-out will be the sensitivity analysis. Conversely, if any of the imputation models have less than 5 observations, then wash-out will be the primary analysis and MI-RD will be the sensitivity analysis. A summary of the number and percentage of subjects who were retrieved drop-outs will be presented by visit for the ST period for both HbA1c and FPG.

4.4.2 Sensitivity analysis for primary endpoint

4.4.2.1 Analysis excluding data following rescue medication initiation/early treatment discontinuation

To assess the robustness of the primary efficacy analysis for the primary endpoint of the change in HbA1c from baseline to Week 26, an additional sensitivity analysis will be performed excluding data following rescue medication initiation or early discontinuation of treatment (i.e., those data will be considered missing and will be imputed together with other missing Week 26 data). This analysis will be performed as for the primary analysis of the primary endpoint but changing the method of imputation as described below.

Multiple imputation for this sensitivity analysis will assume MAR within each treatment regimen. This means that the distribution of missing data in subjects who discontinued treatment early or who used rescue medication prior to Week 26 will be imputed based on data from other subjects in the same treatment regimen who completed the ST treatment and did not use rescue during the ST period.

The following two steps will be used:

- Step 1: Prior to imputation, the MCMC method will be used as described in Section 4.1.12.1. The imputation model will include factors and covariates in the following order: indicators of randomisation strata and baseline HbA1c as well as Week 6, Week 12, Week 20 and Week 26 HbA1c.
- Step 2: Using the monotone datasets generated as described above, impute missing Week 26 HbA1c data using multiple imputation under MAR hypothesis (as described in Section 4.1.12.5).

Dummy coding of categorical variables will be implemented prior to imputation as described in Section 4.1.12.

Downstream steps (analysis of each imputed data set using the ANCOVA model described in Section 4.1.9, and combining results as described in Section 4.1.12.4) will be performed as for the primary analysis.

4.4.2.2 Analysis based on Evaluable Subjects Data Set

To assess the robustness of the primary efficacy analysis for the primary endpoint of the change in HbA1c from baseline to Week 26, an additional sensitivity analysis using the same approach as the sensitivity efficacy analysis in Section 4.4.2.1 may be performed using the Evaluable Subjects Data Set if greater than 10% of the subjects for any treatment group or placebo in the Randomised Subjects Data Set have relevant protocol deviations. For this analysis all HbA1c collected after relevant protocol deviations onset or after rescue medication initiation/early discontinuation of treatment will be set to missing prior to multiple imputation process. An ANCOVA model will be used for this analysis.

4.4.2.3 Missing data patterns

The pattern of missing data for the primary endpoint will be provided (as produced by PROC MI in SAS). This summary arranges the response data (in this case HbA1c) into "patterns" (for example, the number and percentage of subjects with no missing data at any visit, or with missing data only for the last visit, or with missing data for the last two visits, and so on) regardless of/excluding values after rescue medication initiation or premature end of study medication, by treatment group. This also provides mean HbA1c by missing data pattern.

In addition, descriptions of missing HbA1c as well as HbA1c data collected following rescue medication initiation or discontinuation study medication will include a description per visit by treatment group during the short-term period of:

- the cumulative number of subjects who discontinued study medication,
- the cumulative number of subjects who discontinued study medication but still on study,
- the cumulative number of subjects rescued,
- the cumulative number of subjects rescued but still on study,
- the cumulative number of subjects rescued or who discontinued study medication,
- the cumulative number of subjects rescued or who discontinued study medication but still on study,
 - the number of subjects rescued or who discontinued study medication but still having a Week t HbA1c value,
 - the number of subjects rescued or who discontinued study medication and missing Week t HbA1c value,

- the cumulative number of subjects withdrawn from study,
- the number of subjects still on treatment, still on study, not rescued but who missed a given visit,
- the number of subjects missing Week t HbA1c value,
- a graphical summary presenting the monotone missing data pattern from baseline to Week 26 presenting HbA1c values regardless of rescue medication initiation as well as presenting HbA1c values collected prior to rescue medication initiation or discontinuation of study medication by treatment group, along with a corresponding summary table.

4.4.2.4 Tipping point analysis

To assess the robustness of the primary efficacy analysis for the primary endpoint of the change in HbA1c from baseline to Week 26, an additional sensitivity analysis using a tipping point will be performed at Week 26 as described in Section 4.1.12.6 for the same ANCOVA model used for the primary analysis (Section 4.4.1).

4.4.3 Subgroup analyses for primary endpoint

4.4.3.1 Analysis of change from baseline in HbA1c at Week 26 within subgroups

The subgroup-by-treatment interaction will be assessed for the primary efficacy endpoint using the MI-WO imputation method and the ANCOVA model used for the primary analysis of the change from baseline in HbA1c at Week 26 with subgroup, and subgroup-by-treatment interaction as additional effects. Separate imputation models for each subgroup will be used. This will be repeated for subgroups based on race, ethnicity, sex, age group (using randomisation strata), region, baseline antidiabetic treatment, baseline HbA1c, and baseline BMI, using the categories defined in the Appendix (Table 19). The adjusted mean changes from baseline, SEs, 95% CIs, and p-value for each subgroup and the nominal p-value for subgroup by treatment interaction will be calculated.

The subgroup by treatment interaction p-value will be calculated as the median p-value from the set of all imputations.

Models for subgroup analyses which evaluate baseline HbA1c level will include terms for the categorised baseline HbA1c level and not (continuous) baseline values.

Statistical significance of a Week 26 treatment regimen*subgroup interaction will be assessed at an unadjusted 0.10 level.

In addition, a forest plot of adjusted mean difference from placebo \pm 95% confidence interval (CI), p-values for each subgroup category and p-value for interaction by subgroup will be displayed.

Subjects with missing data for the grouping variable will be excluded from the corresponding subgroup analysis. For each subgroup, if, in any treatment group, the number of subjects is less than 10 for a subgroup category, adjusted estimates and their differences and corresponding

statistics will not be displayed for that subgroup, and only descriptive statistics will be presented for that category and included in the analysis results. Interaction p-value will not be provided either.

For baseline antidiabetic treatment subgroup, if the number of subjects within ‘insulin only’ or ‘metformin + insulin’ category is less than 10, then these two categories will be grouped into ‘insulin +/- metformin’. In case of non-convergence because of sparse data, subsequent backup imputation models will be used collapsing the randomisation strata of background medication as defined in Section 4.1 and collapsing the region into ‘North America + Europe’ and ‘Rest of the World’.

4.4.3.2 Metformin subgroup analysis for primary analysis of change from baseline in HbA1c at Week 26

The ANCOVA model used for the primary analysis (Section 4.4.1) of the change from baseline in HbA1c at Week 26 will also be repeated for the subgroup of subjects on a stable baseline dose of metformin IR or XR (with or without insulin). The same multiple imputation method used for the primary analysis of the endpoint will be used for this subgroup analysis. The indicator for background medication used in the multiple imputation step for insulin only and insulin with metformin will be grouped as defined in Section 4.1.12.

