1.2 Study design

The proposed study is a 26-week Phase 3b, multicentre, randomised, placebo-controlled, double-blind, parallel-group study with a 26-week safety extension period to evaluate the safety and efficacy of dapagliflozin (5 mg and 10 mg), and, separately, saxagliptin (2.5 mg and 5 mg) in paediatric subjects with T2DM, and an additional post-study visit at Week 104 for assessment of measures of growth and maturity.

This study will consist of 4 study periods:

- (i) **Screening period.** This period starts with enrolment and ends at the start of the lead-in period.
- (ii) **Lead-in period.** During this 2-week period, subjects will be instructed on a diet and exercise program (in accordance with the American Diabetes Association [ADA] or similar local guidelines) to be followed for the study duration. Subjects will maintain their baseline types and/or doses of antidiabetic therapy throughout the study. No placebo or study medication will be provided during the lead-in period.
- (iii) **26-week double-blind short-term (ST) treatment period.** On the Day 1 visit, subjects who meet all protocol-specific enrolment and randomisation criteria will be randomised.
- (iv) **26-week double-blind long-term (LT) treatment period.** After completing the ST treatment period, all subjects will enter the 26-week LT treatment period.

The 52-week treatment period will be referenced as the ST+LT treatment period.

The **Randomised withdrawal period** is defined, for those subjects eligible for the 3rd randomisation, as the time from 3rd randomisation (Week 32 or Week 40) until end of LT period (Week 52).

Subjects who discontinue IP treatment before the end of the study treatment period will enter a non-treatment, follow-up phase in which subjects will follow their visit schedules with modified assessments until study completion.

In addition, there will be 2 post-study visits:

- (i) **Week 56** (phone visit), to assess AEs and serious adverse events (SAEs).
- (ii) **Week 104** (office visit), to assess measures of growth and maturity, height, weight, AEs and SAEs.

Approximately 243 paediatric subjects aged 10 to below 18 years of age will be randomised in a 1:1:1 ratio to receive dapagliflozin 5 mg, saxagliptin 2.5 mg, or placebo. Approximately 81 subjects will be randomised to each treatment arm.

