1.3 Number of subjects

The sample size for this study was selected to be consistent with the research hypotheses.

Dapagliflozin and saxagliptin will be compared with placebo separately. Within each group of hypotheses, multiplicity adjustment with respect to the comparisons will be made using a hierarchical approach. No comparisons between dapagliflozin and saxagliptin will be performed.

The sample size for this study is based on the ability to detect a 0.75% improvement over placebo for dapagliflozin or saxagliptin in change from baseline in HbA1c at Week 26 (ST) with approximately 80% power for each comparison at a two-sided alpha level of 0.05. If 243 paediatric subjects are randomised and analysed, and each treatment compared to placebo at a 2 sided alpha=0.05 level, this will provide approximately 80% power for each comparison to detect a 0.75% reduction in HbA1c change from baseline versus placebo assuming a standard deviation of 1.7%.

Day 1 Randomisation will be stratified based on the baseline anti-diabetic treatment regimen (stable baseline dose of metformin [IR or XR], a stable baseline dose of insulin, or a stable combination of metformin [IR or XR] and insulin), sex, and age (≥ 10 to < 15 years, ≥ 15 to < 18 years).

The standard deviation estimate of 1.7% is based on a blinded review of the ongoing study data.

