8.8 Subgroups

Table 19 Subgroups analyses

Group variable	Subgroups
Race	White Non-White
Ethnicity	Hispanic or Latino Not Hispanic or Latino
Sex*	Male Female
Subject age*	≥ 10 and < 15 years ≥ 15 and < 18 years
Baseline HbA1c	< 8% ≥ 8%
Geographic region	North America Latin America Europe Asia/Pacific
Antidiabetic background medication*	Metformin only Insulin only Metformin + Insulin
Baseline body mass index	< 30 kg/m ² ≥ 30 kg/m ²

* based on randomisation strata.

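### The baseline-HbA1c subgroup model drops the continuous baseline covariate, at a small cost in precision and in consistency with the other forest-plot rows

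*SAP*

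**What the plan says.** SAP 4.1.9 and 4.4.1 set the primary analysis as an ANCOVA of change in HbA1c with baseline HbA1c as a covariate, plus treatment and the randomisation strata. SAP 4.4.3.1 builds each subgroup model from that ANCOVA by adding the subgroup and its interaction with treatment. Eight factors are listed. For one of them, "Baseline HbA1c" in Table 19 (SAP 8.8), the model "will include terms for the categorised baseline HbA1c level and not (continuous) baseline values". The table gives it two levels, split at 8%. No reason is stated for the exception.

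SAP 4.4.3.1 asks for adjusted mean changes per category, a forest plot of differences from placebo, and an interaction p-value read at an unadjusted 0.10. SAP 4.5.2.2 applies the same approach, with weights, to the low-dose/high-dose regimen comparison. Day 1 randomisation is stratified on background treatment, sex and age, not on HbA1c (SAP 1.3).

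**The concern.** Patients qualify with a screening HbA1c anywhere from 6.5% to 10.5%, so a split at 8% leaves real spread in baseline inside each category. The outcome is Week 26 minus baseline, which makes baseline a natural covariate. With the continuous term removed, nothing in the analysis model adjusts for baseline differences between arms within a category, and stratification does not balance them either.

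Two things are at stake. The first is precision in already small subgroups. The second is comparability: the forest plot would place these two rows beside rows from models that keep continuous baseline, and the plan provides no note to tell the reader so.

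**Working it through.** **Inputs from the documents.** Effect: "ability to detect a 0.75% improvement over placebo". Power and alpha: "with approximately 80% power for each comparison at a two-sided alpha level of 0.05". SD: "The standard deviation estimate of 1.7% is based on a blinded review of the ongoing study data". Size: "Approximately 81 subjects will be randomised to each treatment arm", with no allowance for dropout ("If 243 paediatric subjects are randomised and analysed").

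**Inputs that are assumptions.** The documents give neither the baseline distribution nor its slope with change. I take baseline as normal, mean 8.1, SD 1.0, truncated to 6.5–10.5; a slope b of change on baseline of 0.3 to 0.7 in absolute size; and about 40 per arm per category, roughly half of 81.

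**1. The plan's own figure.** SE = 1.7 × √(2/81) = 0.267. 0.75/0.267 = 2.81, and 2.81 − 1.96 = 0.85, which gives power 0.80. The stated 80% reproduces and does not depend on this point.

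**2. Spread left inside the categories.** The truncated distribution has mean 8.19 and variance V = 0.744. The within-category SDs are 0.40 (below 8%; variance 0.162) and 0.57 (8% or above; variance 0.328), with 56.7% of patients in the upper category. Pooled within-category variance = 0.433 × 0.162 + 0.567 × 0.328 = 0.256. As a share of the total, 0.256/0.744 = 34%, so the category absorbs about 66%. Other assumed shapes (uniform, or truncated normal with other means and SDs) leave 30% to 34%.

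**3. Loss of precision.** If 1.7 is the SD within a category before continuous adjustment, the SE ratio (category only over continuous kept) is 1/√(1 − b²v/1.7²), where v is the within-category variance.

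| b | below 8% | 8% or above | pooled |
|---|---|---|---|
| 0.3 | +0.25% | +0.5% | +0.4% |
| 0.5 | +0.7% | +1.4% | +1.1% |
| 0.7 | +1.4% | +2.9% | +2.3% |

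If 1.7 is instead the overall SD, the ratio is √(1 + b²v/(1.7² − b²V)). The worst case is then √(1 + 0.161/2.525), or +3.1%. The range is therefore about 0.3% to 3%.

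**4. On the HbA1c scale.** With 40 per arm, SE = 1.7 × √(2/40) = 0.380 and the 95% half-width is 1.96 × 0.380 = 0.745. In the upper category, keeping the covariate narrows that to 0.741 (b = 0.3) or 0.724 (b = 0.7). The gain is 0.004 to 0.021 points.

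**5. Chance imbalance is the same quantity.** A one-SD imbalance moves the difference by b × SD × √(2/40): 0.04 to 0.09 points for 8% or above, and 0.03 to 0.06 below 8%. At b = 0.7 in the upper category, 0.090² / 0.380² = 5.6% of the variance, and 1/√(1 − 0.056) = 1.029. That is the +2.9% in the table, so the imbalance is already inside the SE.

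**6. Stronger correlations.** In terms of the within-arm correlation ρ between baseline and change, across the assumed shapes, the SE rises 1.5–1.6% at ρ = 0.3, 4.8–5.4% at 0.5 and 8–9% at 0.6. Within-category power for a 0.75 difference with 40 per arm goes from 0.54 to 0.53 at ρ = 0.3 and from 0.63 to 0.58 at ρ = 0.5. Slopes of 0.3 to 0.7 correspond to ρ = b × 0.863/1.7, or 0.15 to 0.36, so the larger figures lie outside the assumed range.

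**The case against.** The best defence has four parts.

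- **The choice is explicit and exploratory.** It is pre-specified, it concerns one of eight subgroup factors and its secondary counterpart, and the interaction p-value is nominal. This stands, and it limits the point to a minor one.
- **The gain is tiny.** At most about 0.02 points of half-width under the main assumptions. This also stands.
- **The simple fix has a flaw.** If uncentred baseline sits beside the category, default adjusted means are evaluated at the overall mean, about 8.2 here. No patient below 8% has that value, so the displayed mean for that category would be an extrapolation. This is correct, but it is an argument for centring within category rather than for dropping the covariate. Treatment differences are the same either way.
- **The baseline range is uncertain.** The 6.5% to 10.5% limits apply at screening. Baseline is the last value on or before first dose (SAP 4.1.1), and Table 6 allows values outside those limits. The truncation is therefore approximate, and the size could move either way.

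A reader might also infer that the trial's strongest prognostic covariate has been given up. The documents do not rank baseline HbA1c against other covariates or give its correlation with the outcome. Adjustment is also reduced rather than lost: the category carries about two thirds of baseline variance under the assumptions, and baseline HbA1c remains in the wash-out imputation model (SAP 4.1.12.3).

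**Conclusion.** The point holds as a minor one about efficiency and consistency. Within each category of the baseline-HbA1c subgroup analysis, the primary model's baseline covariate goes unadjusted, and those rows are not modelled like the rest of the forest plot. The price is intervals about 0.3% to 3% wider, conditional on the assumed baseline distribution and slopes; only the SD of 1.7 comes from the documents.

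Two stronger readings are not supported. One is that imbalance biases the subgroup effects: under randomisation it is chance error already counted in the standard error, not a second harm on top of lost precision. The other is that confirmatory conclusions are touched: the primary ANCOVA keeps continuous baseline, and the hierarchy in SAP 4.5.1 does not use this model.

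**What to change.** In SAP 4.4.3.1, and through it 4.5.2.2, fit the baseline-HbA1c subgroup model with strata, treatment, category, category-by-treatment, and continuous baseline HbA1c centred at the category mean taken over both arms. State that adjusted means are evaluated at each category's own mean baseline. Because the category term absorbs the centring, the treatment differences and the interaction test are the same as with uncentred baseline.

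The cost is one model term and that note; no new data are needed. If the sponsor prefers the category alone, the SAP should give the reason and footnote the forest plot to say that these rows are adjusted differently.
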